3.5 Outcomes

1. Primary Outcome: Change of Axial length (AL, mm) at 12-month follow-up
2. Secondary Outcome: Change of cycloplegic spherical equivalent (SE, D) at 12-month follow-up
3. Optional Indicators:

Changes of uncorrected visual acuity (UCVA), best-corrected visual acuity (BCVA), intraocular pressure, etc.;

Changes of corneal thickness (CT), anterior chamber depth (ACD) and lens thickness (LT);

Observe macula and the structure of fundus around the optic disc;

Observe the choroid/retinal thickness of the fundus;

Compliance index: frequency of equipment uses.

[figure not shown]

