7) Slit-lamp examination: Slit-lamp examination will be used to examine the anterior segment, lens, vitreous, and fundus, and any abnormalities will be recorded.

8) Optical coherence tomography (optional): SS-OCT fundus image acquisition and data processing: using swept source OCT (DRI OCT-1 Atlantis, Topcon) 9 Line Radial follow-up mode to scan and collect images to obtain fundus pictures and fundus tissue tomographic images. Before the collection, the subjects should be asked to sit still for a while, avoid taking coffee and drinks; during collection, doctors should pay attention to correct the axial magnification; researchers should concentrate on collection time to avoid the influence of the time rhythm fluctuation of choroidal thickness. After the choroidal boundary is automatically segmented by the machine's built-in software,

manual verification and correction are carried out, and the choroidal thickness data of 9 regions of the fovea and the inner, middle and outer rings (upper, lower, nasal, and temporal) are obtained.

2. Follow-up Examinations:

- 1) Questionnaire: A questionnaire on adverse events following the intervention will be administered at each follow-up visit and unexpected visits for children in the intervention group. Children and their parents/guardians will be asked about the side effects, including but not limited to short-term glare, flash blindness, and afterimages.
- 2) Visual acuity: An ETDRS chart (Guangzhou Xieyi Weishikang, Guangzhou, China) with standard illumination will be used to measure distance visual acuity. Visual acuity measurement is performed at a distance of 4 meters. Uncorrected visual acuity will be measured for each follow-up visit, best corrected visual acuity will be measured for the baseline, 6-month and 12-month follow-up visit.
- 3) Ocular biometric measurements via IOLMaster: IOLMaster will be used to measure the axial length of both eyes. Five measurements will be taken for each eye. The axial length measurement will be based on the mean of these five values if the desired precision (<0.05 mm) is achieved.
- 4) Cycloplegia: Cycloplegia will be induced with three drops of 1% cyclopentolate administered at the 0, 5th, and 20th minute to each eye. The light reflex and pupil dilation will be checked after an additional 15 minutes. Dilation and light reflex status will be recorded and full cycloplegia will be justified if the pupil dilates to 6 mm or greater and the light reflex is absent.

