- 5) Cycloplegic auto-refraction: Cycloplegic auto-refraction will be conducted using an auto-refractor (KR-8800, Topcon, Tokyo, Japan). The same auto-refractor will be used throughout the study. It will be calibrated before each examination session to ensure there is no equipment drift during the long follow-up process.
- 6) Slit-lamp examination: Slit-lamp examination will be used to examine the anterior segment, lens, vitreous, and fundus, and any abnormalities will be recorded.

7) Optical coherence tomography (optional): Swept Source-OCT (DRI OCT-1 Atlantis, Topcon) will be used to capture the macular scan. Shooting mode: 12 mm radial scan mode (follow up mode).

8) Safety assessment

- ① The incidence of allergic reactions;
- ② Afterimage duration exceeds 5 minutes;
- ③ Decreased near visual acuity;
- ④ Levels of side effects such as photophobia and blurred vision;
- ⑤ Increased intraocular pressure, headache, nausea and vomiting, etc.

Follow-up Schedule

(1) Visit 1: Screening period (-7~0 days)

- 1) Sign the "Informed Consent";
- 2) Record the general information of the patient;
- 3) Record the medical history;
- 4) Perform visual inspection, axial inspection, intraocular pressure inspection, equivalent spherical lens measurement, slit lamp inspection, OCT inspection;
- 5) Review the inclusion and exclusion criteria;
- 6) Record the combined/concomitant medication;

(2) Visit 2: Enrolment and randomization (day 0)

- 1) Randomly group, and the intervention group will receive experimental devices;
- 2) Record device defects;
- 3) Record the combined/concomitant medication;

(3) Visit 3: Day 30±14

- 1) Perform visual inspection, axial inspection, and intraocular pressure inspection;
- 2) Record the combined/concomitant medication;
- 3) Record adverse events/device defects.

(4) Visit 4: Day 90±14

- 1) Perform visual inspection, axial inspection, and intraocular pressure inspection;

2) Record the combined/concomitant medication;

3) Record adverse events/device defects.

(5) Visit 5: Day 180±14

1) Perform vision examination, axial examination, intraocular pressure examination, equivalent spherical lens, slit lamp examination, and OCT;

2) Record the combined/concomitant medication;

3) Record adverse events/device defects.

(6) Visit 6: Day 270±14

1) Perform visual inspection, axial inspection, and intraocular pressure inspection;

2) Record the combined/concomitant medication;

3) Record adverse events/device defects.

(7) Visit 7: Day 365±14

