4.3 Process of the practice

Schedule of events table

Phase	Period of Filter	Enrollment and randomization	Period of Treatment				
Visit Time	Visit 1	Visit 2	Visit 3	Visit 4	Visit 5	Visit 6	Visit 7
Observed Time Point	Day-7~0	Day 0	Day 30±14	Day 90±14	Day 180±14	Day 270±14	Day 365±14 天
Demographic data	√						
History-taking	√						
Examination of Distant Vision	√		√	√	√	√	√
Examination of Axial	√		√	√	√	√	√

Intraocular Pressure (IOP)	✓		✓	✓	✓	✓	✓
Spherical Equivalent (SE)	✓				✓		✓
Examination with Slit-lamp	✓				✓		✓
OCT	✓				✓		✓
Sign Informed Consent	✓						
Determine Inclusion/Exclusion Criteria	✓						
Random Grouping	✓						
Distribute Equipment		✓					
Record Device Defects		✓	✓	✓	✓	✓	✓
Record Concomitant Medications	✓		✓	✓	✓	✓	✓
Record Adverse Events	✓		✓	✓	✓	✓	✓
End of Practice							✓

5. Data entry and Analysis

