5.2 Statistical analysis plan

The intention-to-treat (ITT) population comprised participants randomly assigned to either group. Data from all participants who attended at least one subsequent follow-up visit were included in the analysis, regardless of treatment or follow-up visit compliance. No imputation was used for the missing data. Individuals who switched to other myopia treatment modalities, such as orthokeratology or atropine eye drops, or discontinued the RLRL treatment, were censored. If a participant had only one eye with a SER exceeding -4.0 D, that eye was selected for the statistical analysis. In cases where both eyes were exceeding -4.0 D, the right eye was chosen for the analysis.

Treatment efficacy was assessed using longitudinal mixed models for primary (changes in AL) and secondary (changes in SER and IOP) outcomes at multiple follow-up visits. The mixed effects model was fitted with a random intercept and random slope for the participant, where the group, visit, group-by-visit interaction, baseline age, sex, and baseline AL were fixed effects. Estimated mean treatment differences and corresponding 95% confidence intervals (CIs) were derived from mixed models. UCVA alterations were classified into three categories: decline by two or more lines, stable (within a line), or improvement by two or more lines. The BCVA at the 12-month and baseline was evaluated against the 20/25 standard.

Sensitivity analyses were conducted to assess the treatment effects of therapy in controlling myopia progression, specifically axial elongation and SER progression, across different baseline SER and age groups.

A longitudinal mixed-model analysis was conducted to assess the relationship between treatment efficacy and compliance within the intervention group. Treatment compliance in the intervention group was measured as a percentage of the total number of assigned treatment sessions.

Safety analyses were performed in the ITT population. All adverse events were reported individually. Six ophthalmologists, one from each center, independently scrutinized the OCT scans for potential structural anomalies.

6.MONITORING

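### SER change has at most two follow-up values per child, too few to identify a correlated random intercept and slope; the 12-month difference stays estimable, but the SER covariance model should be restated

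*Combined protocol and SAP*

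**What the plan says.** Section 5.2 specifies a single covariance model for all longitudinal outcomes: "The mixed effects model was fitted with a random intercept and random slope for the participant". It covers the primary outcome, AL change, and "secondary (changes in SER and IOP) outcomes at multiple follow-up visits". The section does not say whether intercept and slope may correlate, what time scale the slope uses, or what happens if the fit fails. What is reported is stated: "Estimated mean treatment differences and corresponding 95% confidence intervals (CIs) were derived from mixed models".

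The SER outcome in Section 3.5 is "Change of cycloplegic spherical equivalent (SE, D) at 12-month follow-up".

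The visit list in Section 4.2 places spherical equivalent at screening, day 180 and day 365. For the visits at days 30, 90 and 270 it says only "Perform visual inspection, axial inspection, and intraocular pressure inspection". The events table in Section 4.3 agrees, with SE ticked at Visits 1, 5 and 7. The general list of follow-up examinations in Section 4.2 includes cycloplegic auto-refraction without naming visits, although for another measure it does name them: "best corrected visual acuity will be measured for the baseline, 6-month and 12-month follow-up visit". It does not contradict the two schedules.

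Section 5.2 also analyses one eye per child and imputes nothing, so SER change has at most two follow-up values per child.

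**The concern.** A random intercept and slope suits five visits. With two it asks more of the data than they hold. If the effects may correlate, the likelihood has a flat direction: many different sets of variance components fit equally well. Software may then report a singular fit or fail to converge, and the analyst has to pick another structure with the data in hand.

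That choice is not neutral. The obvious simplifications (independent effects, or no slope) can understate the 12-month standard error for SER, the secondary outcome named in Section 3.5. For independent effects, whether this happens depends on how time is coded, which the SAP does not state.

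**Working it through.** **Plan's own figures.** The documents give no figure for the SER model. The sample size in Section 3.6 concerns AL and is reproduced: SD 0.40 mm, difference 0.20 mm, two-sided 5% (assumed two-sided), 90% power gives 2 × (1.960 + 1.282)² × (0.40/0.20)² = 84.1, so 85 per group by the normal formula; the t-test gives 85.03, so 86. Then 172/0.9 = 191.1, so 192. Nothing below changes this.

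**1. Counting.** Let g00, g01, g11 be the intercept variance, covariance and slope variance, s² the residual variance, and t1, t2 the two visit times:

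- V11 = g00 + 2·t1·g01 + t1²·g11 + s²
- V12 = g00 + (t1 + t2)·g01 + t1·t2·g11
- V22 = g00 + 2·t2·g01 + t2²·g11 + s²

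That is three equations in four unknowns. Jacobian ranks at nominal days:

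| Outcome | Random effects | Rank / parameters |
|---|---|---|
| SER (180, 365) | correlated | 3 of 4 |
| SER (180, 365) | independent (g01 = 0) | 3 of 3 |
| AL, IOP (30, 90, 180, 270, 365) | correlated | 4 of 4 |

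A baseline change fixed at zero has no variance and adds no equation.

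**2. The flat direction.** Assume V11 = 0.09, V12 = 0.12, V22 = 0.25 D², with t = 0.5 and 1 year. Every s² from 0 to 0.0258 (the smallest eigenvalue of V) fits exactly. Two examples:

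- s² = 0.005: g00 = 0.105, g01 = −0.11, g11 = 0.36. V11 = 0.105 − 0.11 + 0.09 + 0.005 = 0.09.
- s² = 0.025: g00 = 0.005, g01 = 0.01, g11 = 0.20. V11 = 0.005 + 0.01 + 0.05 + 0.025 = 0.09.

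V12 and V22 are also the same in both.

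**3. The reported quantity.** In one simulated data set (96 per arm, 10% missing at 12 months, assumed variances), points along the flat direction gave the same REML value, the same 12-month difference (0.482 D) and the same standard error (0.075) as an unstructured fit.

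**4. Actual visit days.** With days spread uniformly over ±14, 172 children and assumed variances, all four components are formally identified. The standard error of s² is 0.0238 when s² = 0.01 (238%) and 0.0237 when s² = 0.02 (118%). On the AL schedule it is about 6%.

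**5. Fit behaviour.** In 30 simulated correlated fits (96 per arm, 10% missing, the V of step 2) 27 reported convergence and 3 did not. In a further 40, 37 raised a singularity, boundary or Hessian warning and 4 did not converge.

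**6. Independent effects as fallback.** Let k = SD at 6 months / SD at 12 months, rho = their correlation, r = t1/t2, with V22 and t2 scaled to 1. Then g11 = (1 − k²)/(1 − r²) and g00 = rho·k − r·g11. The fit reproduces V unless g00 would be negative, that is unless rho·k < c(1 − k²), with c = r/(1 − r²). When g00 is held at zero, the fitted V22 is too small, and type I error = 2Φ(−1.96·√(fitted V22 / true V22)).

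Example, months, k = rho = 0.5: g11 = 0.75/0.75 = 1 and g00 = 0.25 − 0.5 = −0.25. Constrained ML gives fitted V22 = 0.880, hence 6.6%.

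The documents give neither k nor rho; both are assumed to lie between 0.5 and 0.9.

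| Slope coding | c | SE too small at rho = 0.5 if k below | Type I error over the range | At k = 0.6, rho = 0.8 |
|---|---|---|---|---|
| Months (6, 12) | 0.667 | 0.693 | 5.0–6.6% | 5.0% |
| Follow-up number (3, 5) | 0.938 | 0.768 | 5.0–7.7% | 5.6% |
| Protocol visit number (5, 7) | 1.458 | 0.843 | 5.0–9.2% | 6.9% |

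All maxima are at k = rho = 0.5.

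**7. Simulation** (86 complete children per arm, 3000 runs, Monte Carlo error about 0.4 points):

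| k, rho | Unstructured | Independent, months | Independent, 5/7 |
|---|---|---|---|
| 0.5, 0.5 | 5.0% | 6.7% | 9.2% |
| 0.6, 0.8 | 4.5% | 4.6% | 6.6% |
| 0.71, 0.7 | 4.6% | 4.6% | 5.6% |
| 0.9, 0.7 | 5.0% | 5.0% | 5.0% |

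**8. Dropping the slope.** A random intercept alone pools the two variances, so fitted V22 = (k² + 1)/2. At k = 0.6 this is 0.680, giving 10.6%; at k = 0.7 it is 0.745, giving 9.1%.

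**The case against.** The strongest reply is that the unidentified components are never reported. The SAP reports mean differences and intervals, and steps 2 and 3 show these do not depend on how the variance is split. That stands, and it limits the concern to what happens when the fit is singular or fails.

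Second, the inflation rests on k, rho and a time coding that the documents do not give. With time in months it is small: on a 5 × 5 grid of k and rho from 0.5 to 0.9, only 2 of 25 points exceed 6%, and none exceeds 5.0% once k is 0.70 or more. Linear progression plus measurement error, including the baseline error shared by both change scores, gives exactly the independent-effects form in elapsed time. The 9.2% needs coding by protocol visit number, and k = rho = 0.5 implies that change in the second half-year has three times the variance of change in the first (0.75 against 0.25) and is uncorrelated with it. All of this stands. The upper figures are bounds under unfavourable assumptions, not expectations.

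Third, the type I simulations used complete data, whereas the plan expects 10% loss and censors children who switch or discontinue treatment. They do not show the rates under that missingness.

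What the reply does not remove is that the stated model asks for more than the plan's own SER schedule can supply, that most of the 40 simulated fits in step 5 raised warnings, and that the SAP offers no next step.

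**Conclusion.** The concern holds, for SER only. With correlated effects and nominal times the four variance components are not identified, whatever the variances. With actual days they are identified only very weakly, and with independent effects they are just identified. The 12-month difference is estimable in every case.

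The practical harm is conditional: a singular or failed fit may force an unplanned model choice. Within the assumed range, type I error under independent effects runs from 5.0% to 6.6% (months) or up to 9.2% (protocol visit numbers). Dropping the slope gives about 9% to 11% at k = 0.6 to 0.7. Confidence is high in the algebra; the error rates depend on assumed k and rho. The AL and IOP models are identified at five visits, and the sample size is unaffected. The point should be settled before analysis, but it does not threaten the primary result.

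**What to change.** Keep the current model for AL and add one sentence for SER to Section 5.2, for example:

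> SER change will be analysed by a repeated-measures model with fixed effects for arm, visit (6 or 12 months, categorical), their interaction, sex, and age and AL at baseline, with an unstructured 2×2 covariance within participant; the estimate is the difference between arms at 12 months with its 95% CI.

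This has three covariance parameters for three estimable quantities, needs no slope time scale, retains the planned fixed effects and targets the outcome in Section 3.5. Naming the degrees-of-freedom method in the same sentence would complete it. The cost is one sentence, with no new data or visits.

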8.2 Plan modification

8.3 Informed consent

8.4 Confidentiality

1. ABSTRACT

Basic information on clinical practice of medical devices:

Device Classification: Class II medical devices

Specification Model: RS-200-1A

Date: September 20, 2020

Sponsor: Zuoguan Medical Devices Co., Ltd. at Suzhou Industrial Park

Practice Title

A Randomized, Controlled, Multi-centre Clinical Study on the Effectiveness and Safety of repeated low-level red-light (RLRL) for myopia control in children and adolescents with high myopia

Practice Purpose

A Study on assessing the effectiveness and safety of RLRL for myopia control in children and adolescents with high myopia.

Subject Population

Subject: Children aged 6-16 with at least one eye with myopia of cycloplegic spherical equivalent refraction (SER) at least -4.0 D

Sample size: 192 subjects are planned to be enrolled and assigned to the intervention group or control group according to a ratio of 1:1

Practice Design

Overall design:

This prospective, single-blind, parallel-group, multi-center randomized clinical trial was conducted at six tertiary hospitals. Participants between 6 and 16 years old with at least one eye with a spherical equivalent refraction (SER) of -4.0 D or greater were recruited. The enrolled participants were randomly placed at a 1:1 ratio into

intervention (RLRL treatment plus single-vision spectacles) or control (single-vision spectacles) groups. The participants attended follow-up appointments 1, 3, 6, 9, and 12 months after the baseline evaluation.

Outcomes:

1. Primary Outcome: Change of Axial length (AL, mm) at 12-month follow-up
2. Secondary Outcome: Change of cycloplegic spherical equivalent (SE, D) at 12-month follow-up
3. Optional Indicators:

Changes of uncorrected visual acuity (UCVA), best-corrected visual acuity (BCVA), intraocular pressure, etc.;

Changes of corneal thickness (CT), anterior chamber depth (ACD) and lens thickness (LT);

Observe macula and the structure of fundus around the optic disc;

Observe the choroid/retinal thickness of the fundus;

Compliance index: frequency of equipment uses.

Safety assessment

- ① Sudden vision loss;
- ② Afterimage time over 5 minutes;
- ③ Side effects such as glare, photophobia and flickering;
- ④ Structural damage to retina: tissue disruption or discontinuity, edema, or other abnormalities in the photosensory layer of the SS-OCT images;
- ⑤ Increased intraocular pressure etc.

Participants selection and exclusion criteria:

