Treatment efficacy was assessed using longitudinal mixed models for primary (changes in AL) and secondary (changes in SER and IOP) outcomes at multiple follow-up visits. Sensitivity analyses were conducted to assess the treatment effects of therapy in controlling myopia progression, specifically axial elongation and SER progression, across different baseline SER and age groups.

A longitudinal mixed-model analysis was conducted to assess the relationship between treatment efficacy and compliance within the intervention group.

Safety analyses were performed in the ITT population. All adverse events were reported individually.

Ethics:

The practice protocol (including the informed consent form) is submitted to the ethics committee for approval, and all subjects entering the trial screening must sign the informed consent form. Researchers should conduct experiments in strict accordance with the experimental protocol and GCP requirements to fully protect the legal rights and safety of the subjects.

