3.3 Randomization and masking

A statistician without contacts with the participants generated the randomization sequence using SAS software (version 9.4; Cary, NC, USA). All eligible participants were randomly assigned to the intervention (RLRL plus SVS) or control (SVS only) groups at a 1:1 ratio. The randomization process adopted central stratification block randomization with block sizes of four or six. Each eligible participant was assigned a number based on their study entry sequence. Random assignment outcomes were

recorded in sealed envelopes with the corresponding sequential numbers written on the covers. Then, an investigator at the main center took custody of the envelopes. Each time an eligible participant's informed consent was acquired, the investigators responsible for group allocation at the six centers contacted the investigator holding the envelopes by telephone. The investigator immediately opened the envelopes and provided information on the group allocation of the newly enrolled participants. Owing to the nature of the intervention, the participants were aware of their assigned treatment groups. However, outcome assessors, including clinical examination technicians, optometrists, ophthalmologists, and statisticians, were blinded to the treatment allocation.

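### The mixed models, as written, omit the randomisation stratum and, for SER and IOP, the outcome's own baseline: a small, easily recovered loss of precision

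*Combined protocol and SAP*

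**What the plan says.** Section 5.2 uses longitudinal mixed models for the primary outcome, change in AL, and for "secondary (changes in SER and IOP) outcomes at multiple follow-up visits". The next sentence specifies a participant random intercept and slope, "where the group, visit, group-by-visit interaction, baseline age, sex, and baseline AL were fixed effects". No centre or stratum appears as a fixed or random effect, and baseline AL is the only ocular baseline. The version in the Abstract names the same three outcomes ("longitudinal mixed models for primary (changes in AL) and secondary (changes in SER and IOP) outcomes") and lists no covariates.

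On allocation, section 3.3 says: "The randomization process adopted central stratification block randomization with block sizes of four or six". It does not name the stratification factor. Assignments were obtained centrally: "the investigators responsible for group allocation at the six centers contacted the investigator holding the envelopes by telephone".

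Both missing baselines are collected. The Visit 1 list in section 4.2 reads "Perform visual inspection, axial inspection, intraocular pressure inspection, equivalent spherical lens measurement, slit lamp inspection, OCT inspection", and the schedule table in section 4.3 agrees.

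The status of IOP varies. The Abstract and section 3.5 list it among the optional indicators, while the analysis text treats it as secondary. Raised IOP is also a safety item in the Abstract ("Increased intraocular pressure etc") and in section 4.2 ("Increased intraocular pressure, headache, nausea and vomiting, etc").

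**The concern.** Stratified allocation balances the arms within strata, so differences between strata drop out of the treatment comparison. A model without the stratum leaves that variation in the residual. The estimate is not biased on average, but its standard error is too large and the test slightly conservative. The trial then reports a wider interval than its design earned.

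The second omission is separate. When a change score is analysed, adjusting for the outcome's own baseline removes the part of the change that the baseline predicts, such as regression to the mean. The AL model already does this. As written, the SER and IOP models adjust for the baseline of a different variable. Type I error stays nominal, but the interval is wider than necessary. The loss is greatest where repeat measurements correlate only moderately, which may be so for IOP.

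**Working it through.** **The plan's own figure.** Inputs from section 3.6: difference 0.20 mm, SD 0.40 mm, α 0.05 (two-sided; one-sided would give 69 per group), power 90%. The normal approximation gives 84.06, so 85 per group. The two-sample t-test has power 0.8999 at 85 and 0.9032 at 86, so 86 is reproduced. 172/0.90 = 191.1, so 192 is reproduced.

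**Stratum term, AL, analytic.** Let v be the share of the variance of 12-month AL change that lies between centres, with allocation stratified by centre. Omitting centre overstates the SE by k = 1/√(1−v), and the true type I error is 2[1−Φ(1.96k)]. The documents give no v, so a range is assumed. The planned 95% half-width is 1.96 × 0.40 × √(2/86) = 0.120 mm.

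| v | k | Type I error | Half-width with centre (mm) |
|---|---|---|---|
| 0.02 | 1.010 | 0.048 | 0.118 |
| 0.05 | 1.026 | 0.044 | 0.117 |
| 0.10 | 1.054 | 0.039 | 0.113 |

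**Stratum term, AL, simulation.** The section 5.2 model was fitted by REML to 192 participants with five visits, 10% monotone loss unrelated to outcome, SD 0.40 and effect 0.20. Assumed inputs: six centres of 72, 40, 28, 24, 16 and 12 that differ in progression rate; blocks of 4 or 6 within centre; random-intercept and residual SD 0.05 each. There were 12,000 runs each for shares of 5% and 10% (Monte Carlo error of type I error 0.002) and 3,000 for 0% (0.004). Each cell shows the planned model / the model with centre and centre-by-visit.

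| Share | SE (mm) | Type I error | Power |
|---|---|---|---|
| 0% | 0.0586 / 0.0586 | 0.049 / 0.049 | 0.930 / 0.927 |
| 5% | 0.0586 / 0.0572 | 0.046 / 0.051 | 0.930 / 0.935 |
| 10% | 0.0586 / 0.0557 | 0.038 / 0.048 | 0.934 / 0.946 |

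The SE ratios, 0.0586/0.0572 = 1.024 and 0.0586/0.0557 = 1.052, agree with the analytic k. The mean error of the estimate is below 0.001 mm throughout.

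**Why the interaction with visit.** A separate simulation at a 10% share compared two ways of adding centre. A main effect alone left the 12-month SE at 0.0577 and type I error at 0.034. Centre-by-visit gave 0.0548 and 0.048. Where centres differ in progression rate, the gap between them grows with time and a constant shift does not capture it.

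**Own baseline, SER and IOP.** Let r be the correlation between baseline and follow-up of the outcome, and ρ the correlation of baseline AL with the outcome's baseline. Assume equal variances, and that follow-up relates to baseline AL only through the outcome's own baseline. In units of the outcome variance:

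- Variance of change given baseline AL only: 2(1−r) − (1−r)²ρ²
- Variance of change given the own baseline: 2(1−r) − (1−r)²
- Q is the first divided by the second. The excess interval width is √Q − 1, and Q is the sample-size multiplier.

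| Outcome | r | ρ | Q | Excess width |
|---|---|---|---|---|
| SER | 0.90 | 0 | 0.20/0.19 = 1.053 | 2.6% |
| SER | 0.98 | 0.7 | 0.039804/0.0396 = 1.005 | 0.3% |
| IOP | 0.5 | 0 | 1/0.75 = 1.33 | 15.5% |
| IOP | 0.5 | 0.3 | 0.9775/0.75 = 1.30 | 14.2% |
| IOP | 0.7 | 0 | 0.60/0.51 = 1.18 | 8.5% |
| IOP | 0.7 | 0.3 | 0.5919/0.51 = 1.16 | 7.7% |
| IOP | 0.7 | 0.7 | 0.5559/0.51 = 1.09 | 4.4% |

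With 86 per group and ρ = 0, the IOP half-width in units of the IOP SD is 0.299 without and 0.259 with its own baseline at r = 0.5, and 0.232 and 0.213 at r = 0.7. Taking r from 0.8 down to 0.4 with ρ = 0 gives intervals 5% to 20% wider, from 1/√0.90 and 1/√0.70.

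**The case against.** The strongest reply is that nothing here threatens validity. The estimate is unbiased, type I error is nominal or conservative, power exceeds 90%, and the simulated power gain for AL is 0.5 points at a 5% share and 1.2 points at 10%. That is correct, and it is why the point is graded minor.

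The AL part is conditional. In section 3.3 the word *central* may mean by centre or centrally run, and the telephone procedure fits either reading. If allocation was not stratified by centre, or centres do not differ, the planned SE and type I error are valid. This stands, so the recommendation refers to the factor actually used.

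The covariate list might describe only the AL model, with each outcome's own baseline intended elsewhere. That is a possible reading, but it leaves the SER and IOP covariates unstated, and the same sentence is still needed.

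The IOP figures rest on assumed correlations, for an outcome on which the trial was not powered and which two sections call optional. This also stands. The safety argument is weak as well: raised IOP is listed as an event-type item, and section 5.2 reports adverse events individually, so the mixed-model interval is not clearly its basis.

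All stratum calculations are for AL; none was run for SER or IOP. That is why the interaction is not asked for in those models.

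Finally, sections 3.3 and 5.2 are written in the past tense. If outcome data have already been seen by arm, a change of model is no longer free of interpretive cost and must be disclosed.

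**Conclusion.** The concern holds as a minor improvement. As written, the models have no stratum term, and the SER and IOP models lack their own baselines.

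- **AL:** the SE is overstated by 0% to 5.4% for a between-centre share of 0% to 10%, if allocation was stratified by centre. The test is slightly conservative and the sample size is unaffected.
- **SER:** the loss is negligible.
- **IOP:** the loss may be moderate, 4% to 15% in interval width for r of 0.5 to 0.7. The 4% end needs baseline AL and baseline IOP to correlate at 0.7; with a correlation of 0 to 0.3 the range is 8% to 15%. With no such correlation, it equals needing 18% to 33% more participants for that comparison.

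The documents supply none of the centre variances, centre sizes or correlations behind these ranges. Confidence in the sizes is therefore medium.

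**What to change.** In section 3.3, name the factor used to stratify randomisation. In section 5.2:

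1. Include that factor in the mixed models. If it is centre, also include centre-by-visit in the primary AL model. The interaction need not be imposed on the SER and IOP models, and centre-by-visit is not needed if allocation was not stratified by centre.
2. Keep baseline AL, add baseline SER to the SER model, and add baseline IOP to the IOP model.

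This costs one or two sentences in 5.2, plus the factor's name in 3.3, and no new data. If the factor is centre, it uses 5 degrees of freedom per model and 20 more in the AL model (5 × 5 visits = 25 in all), plus one term for each own baseline. In the simulation the 25 AL terms cost almost nothing when centres did not differ: SE 0.0586 either way, and power 0.927 against 0.930, even with a centre as small as 12. If outcomes have already been examined by arm, date the change and disclose it.
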